# 5.0 DATA ACQUISITION, TRANSFER AND ANALYSIS

# 5.1 **Data Acquisition**

Electronic case report forms (eCRF) are considered confidential data. The Alcresta data management vendor will provide user access and training to investigative sites on the use of the eCRF system. Subject data will be entered into the eCRF by site staff using a secure, web-based electronic data capture application. Clinical data required by the protocol will be captured on the eCRF and supported by source documentation at site. The site PI will prepare and maintain adequate and accurate medical histories designed to record all observations and pertinent study data for each subject.

Title: Absorption and Safety with Sustained Use of Relizorb™ Evaluation (Assure) Study in Patients With Cystic Fibrosis Receiving Enteral Feeding

To ensure data accuracy, eCRF entry for individual subjects should be completed as soon as possible after the study visit. Site staff should enter information on the eCRF according to the completion guidelines provided by the Alcresta data management vendor. The site PI is ultimately responsible for all information collected on enrolled subjects and must ensure data is reviewed and verified for completeness and accuracy. The signature of the site PI or subinvestigator indicates formal approval of all data entered on the eCRF.

The Alcresta data management vendor will retain eCRF data and corresponding audit trails. A copy of the final archival eCRF in the form of a compact disk or other electronic media will be placed in the Investigator Site File.

# 5.2 Data Transfer

Alcresta, in collaboration with the data management vendor, will be responsible for the electronic transfer of external laboratory data according to fully executed data transmission agreements, data management plans or other study documentation.

# 5.3 Analysis of Fatty Acid Absorption

The concentration of LCPUFAs such as DHA and EPA in plasma is the primary determination supporting the primary endpoint of fat absorption and will be analyzed using UPLC-MS expressed as ug/mL. The relative levels of LCPUFAs such as DHA and EPA in erythrocyte membrane and the overall plasma fatty acid profile also support the primary endpoint and will be analyzed using GC/MS expressed as g/100 g FA.

#### 6.0 SAFETY OVERVIEW

# 6.1 Monitoring of Adverse Events

All study staff are responsible for ensuring that complete safety data has been recorded on the eCRF. Medical assessments must be performed during each scheduled study visit and serve as the primary basis for identifying an UADE. Although spontaneous or elicited medical complaints will likely constitute the majority of UADEs, any non-scheduled visit to a healthcare provider, or the initiation of a new medication, should trigger additional questioning as to the occurrence of an AE or UADE.

### 6.2 Adverse Events

An adverse experience (AE) is defined as any untoward medical occurrence in a subject, regardless of its causal relationship to the investigational device. An AE can therefore be any unfavorable and unintended sign (including abnormal laboratory

Title: Absorption and Safety with Sustained Use of Relizorb™ Evaluation (Assure) Study in Patients With Cystic Fibrosis Receiving Enteral Feeding

findings), symptom or disease experienced with use of the product, whether or not it is related to the product. This includes any newly occurring event or a previous condition that has increased in severity or frequency since the use of Relizorb.

# 6.2.1 Causal Relationship

All AE must be assessed for causality in reference to Relizorb use. When entering data for a reported AE, the site PI will be asked to assess the relationship of Relizorb use to the AE. Causality will be categorized according to the following criteria:

Not Related: There is no medical evidence to suggest the event may be

related to Relizorb use, or there is another more probable

medical explanation.

Possibly Related: An event, including laboratory test abnormality, with a temporal

relationship to Relizorb use that makes a causal relationship improbable and which other medications, events or underlying

disease provide a plausible explanation.

Probably Related: The event occurred within a reasonable time sequence to using

Relizorb, but could be explained by concurrent disease or other

medications or events.

**Related:** There is strong medical evidence to suggest that the AE is related

to Relizorb use.

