# 7.2.1 Stopping Rules

Relizorb is a low risk medical device, and the patient population under study is at relatively low risk for a severe adverse experience. Therefore, there are no prospective stopping rules for this study.

Title: Absorption and Safety with Sustained Use of Relizorb™ Evaluation (Assure) Study in Patients With Cystic Fibrosis Receiving Enteral Feeding

The Alcresta Chief Medical Officer will review all UADEs as they occur. In addition, every 30 days all UADEs will be reviewed in aggregate starting from the first subject enrolled until the last subject has completed the study. Based on this planned surveillance, the Alcresta Chief Medical Officer will convene a teleconference with the chair of the Data Safety Monitoring Board (DSMB) as soon as possible if any of the following occur:

- Death of any subject in the study, regardless of causality,
- Two occurrences of the same UADE where causality has been assigned to Relizorb use by the site PI, or more than three occurrences of the same UADE regardless of causality,
- A trend emerges in the occurrence of similar UADEs.

If either the Alcresta Chief Medical Officer or the chair of the DSMB has a concern regarding the safety of study subjects, the Chief Medical Officer will convene a teleconference with the DSMB and the site PIs as soon as possible to discuss the potential safety issue. Possible outcomes of the teleconference include:

- Continuation of the study with no change in study conduct if it is determined that there is no safety issue,
- Placing the study on clinical hold until the study protocol can be modified to mitigate the safety issue,
- Termination of the study.

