9.1 Adverse Events

All AEs will be coded using the Medical Dictionary for Regulatory Activities (MedDRA Version 18.0 or most recent version).

AEs will be summarized by MedDRA system organ class and preferred term. Separate columns will be included in the AE summary table for AEs starting under the treatment by Standard of Care, and starting during RELiZORB treatment.

For all AEs, the event will be summarized under the treatment (Standard of Care, RELiZORB) the event started in and in the total column. The AE is assigned to the standard of care or RELiZORB based on the start date of the adverse event.

- If the start date of the event is before the first administration of RELiZORB, the event will be summarized under Standard of Care.
- If the start date of the event is on or after the first administration of RELiZORB, the event will be summarized under RELiZORB.
- If the start and end date of the event are both missing, the event will be summarized under both SOC and RELiZORB.

In a general overview of AEs, events will be summarized by treatment for the following items:

- All AEs
- Serious Adverse Events (SAEs)
- AEs by relationship
- AEs leading to discontinuation of enteral feeding
- AEs by maximum severity
- UADEs
- UADEs by relationship
- UADEs leading to discontinuation of enteral feeding
- UADEs by maximum severity

Missing and partially missing AE start and/or stop dates will be imputed, for the purpose of statistical analysis, according to the specifications described in Section 6.2.

Summaries of incidence rates (frequencies and percentages) of individual AEs by MedDRA System Organ Class and preferred term will be prepared. UADEs and SAEs will not be included in summaries of AEs, but will be summarized separately. Each subject will be counted only once within each level of summary (system organ class and preferred term).

Adverse events that lead to discontinuation of enteral feeding will be summarized and listed separately.

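### Protocol 6.2.1 defines *Possibly Related* as causally improbable, so adverse event counts by relationship depend on whether a site codes from the label or from the definition

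*Protocol*

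**What the plan says.** Protocol 6.2.1 (Causal Relationship) gives four labels, each with a definition.

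- *Not Related*: no medical evidence that the event may be "related to Relizorb use, or there is another more probable" medical explanation.
- *Possibly Related*: a temporal "relationship to Relizorb use that makes a causal relationship improbable", where something other than the device offers a plausible explanation.
- *Probably Related*: the event follows device use within a reasonable time, "but could be explained by concurrent disease or other" factors.
- *Related* sets the highest bar: "There is strong medical evidence to suggest that the AE is related" to the device.

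Protocol 7.7 (Safety Analysis) returns to the scale. It describes *Related* simply as an association between the event and device use, and names the two middle categories without defining them.

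The categories are used in several places. Protocol 7.7 plans AE and UADE summary tables by causal relationship. SAP 9.1 lists "AEs by relationship" and the UADE equivalent in its overview. SAP 9.1.1 keeps each subject's strongest relationship, and SAP Table 14.3.2.2 shows UADEs by relationship. Protocol 7.2.1 (Stopping Rules) has the sponsor's Chief Medical Officer contact the DSMB chair on "Two occurrences of the same UADE where causality has been assigned to Relizorb use by the site PI", or on more than three occurrences of the same UADE whatever the causality.

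The SAP gives no causality definitions and no related/not-related cut, and SAP section 10 (Changes from Planned Analysis) does not touch the subject.

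**The concern.** A causality scale is useful only if each label means what its definition says, the categories do not overlap, and they run in order. In 6.2.1 the second category fails the first two tests. An investigator who reads the label will use it for an event the device might have caused. One who reads the definition will use it for an event the device probably did not cause. Both follow the protocol.

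This matters more than usual because the study is open label and single arm, so no concurrent control rate shows what background illness would have produced. Attribution rests on the investigator, at approximately 10 sites. Protocol 6.2.2 attributes the anticipated events to GI complications inherent in CF, so an alternative explanation will often be available, and that is where the definitions are unclear. At stake are the relationship tables and, more narrowly, one of the conditions for contacting the DSMB chair.

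**Working it through.** No arithmetic beyond the trigger counts applies: the documents give no event counts by category and no figure to reproduce. The check sets the definitions against their labels, against each other, and against their uses.

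**Step 1: label against definition.**

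| Label | What 6.2.1 requires | Agreement |
|---|---|---|
| *Not Related* | No evidence, or a more probable alternative | Agrees |
| *Possibly Related* | Timing makes causation improbable, and a plausible alternative exists | Contradicts |
| *Probably Related* | Reasonable timing, other causes could explain it | No contradiction, but nothing says that device causation is likely |
| *Related* | Strong medical evidence | Agrees within 6.2.1, but 7.7 asks only for an association |

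**Step 2: overlap and gap.** Consider four hypothetical events and code each from the definitions alone.

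| Event | Timing | Alternative cause | Evidence for the device | Definitions met |
|---|---|---|---|---|
| A | Makes causation improbable | Plausible and more probable | Weak | *Not Related* and *Possibly Related* |
| B | Reasonable | Could explain it | Moderate | *Probably Related*; also *Not Related* if the alternative is judged more probable |
| C | Reasonable | None | Less than strong | None |
| D | Reasonable | None | Strong | *Related* |

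Event A meets two definitions, so the categories are not mutually exclusive. Event C meets none, provided reasonable timing counts as some medical evidence: *Not Related* then fails, both middle definitions refer to an alternative explanation, and *Related* needs strong evidence. A site would have to choose a label for C without support from the text.

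**Step 3: effect on counts.** A count pooling *Possibly*, *Probably* and *Related* would include events defined as causally improbable. A count pooling only *Probably* and *Related* would still include events that other causes could explain. The boundary with *Not Related* is not fixed either, because of event A. The strongest-relationship rule in SAP 9.1.1 can be applied mechanically, since the labels ascend, but it inherits the uncertainty about what the middle labels mean.

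**Step 4: effect on the DSMB contact trigger.** With causality assigned to the device, the condition is met at 2 occurrences of the same UADE. Without it, more than three are needed, so at least 3 + 1 = 4. The text does not say whether *Possibly* or *Probably* counts as assigned. The ambiguity therefore bites when there are 2 or 3 occurrences of the same UADE coded in those categories.

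**Step 5: search for a repair.** Protocol 7.7 defines neither middle category and adds the looser account of *Related*. The SAP text supplies no definitions. Nothing in the documents resolves the conflict.

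**The case against.** The case on the other side limits the point considerably.

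First, a reader might infer that two of the four categories are shifted up one level. The documents do not support that. An event can be probably due to the device and still have a possible alternative, so the *Probably Related* wording is uninformative rather than contradictory. Speaking of a shift also presupposes an outside reference scale that the protocol does not adopt. There is one direct contradiction.

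Second, a reader might infer that the related-AE counts, or the safety results at large, cannot be interpreted. The SAP specifies no pooled related count, and if all four categories are shown, readers can apply the printed definitions. Relationship is not named in any safety endpoint (Protocol 3.2, SAP 2.2.1). The split into Standard of Care and Relizorb periods uses start dates, not causality. GI tolerability is assessed by diary, which Protocol 4.9.11 calls the basis of the primary safety endpoint. All of this stands.

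Third, a reader might infer that ordinary GI events will trip or evade the DSMB trigger through miscoding. That is unlikely. A UADE must be serious and not previously identified in nature, severity or degree of incidence (Protocol 6.3), and the common GI complaints are listed as anticipated. Any death or an emerging trend also prompts contact. The Chief Medical Officer evaluates each UADE within 24 hours (Protocol 4.8.1) and all UADEs in aggregate every 30 days (Protocol 7.2.1), and the consequence is a teleconference. The exposed window is narrow, though real.

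Fourth, the eCRF wording and completion guidelines are not in the documents, so they may have steered sites to one reading. That is possible and cannot be checked. It does not cure the protocol text, which is the governing definition.

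**Conclusion.** The point holds as a wording defect in an operative classification rule. *Possibly Related* contradicts its label and overlaps *Not Related*; *Probably Related* gives no basis for its label; one kind of event has no category; and *Related* has two definitions of different strength.

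Its reach is AE and UADE counts by relationship, mainly the two middle categories and any related/not-related split, plus one DSMB contact condition at 2 or 3 occurrences of the same UADE. Total AE counts, severity, the GI diary and efficacy are unaffected. The share of events affected is unknown, because no counts by category and no eCRF instructions are available. The conclusion assumes that sites work from 6.2.1 and that no guideline outside these documents overrides it. It should be corrected, since the change is specific and cheap.

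**What to change.** Reword Protocol 6.2.1 so that each definition supports its label and the four or five categories are mutually exclusive and ordered. Move the text about improbable causation to *Not Related* or to a new *Unlikely* category. Use the text about other possible explanations for *Possibly Related*. Define *Probably Related* as more likely than not due to the device, which also gives event C a home. Bring the description of *Related* in 7.7 into line with 6.2.1.

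In the SAP, state which categories count as related in any pooled table. Sections 6.2.1 and 7.2.1 of the protocol must be reconciled on which categories count as causality assigned to the device for the DSMB contact condition.

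Do not re-code events already entered. The SAP is dated 29-Jun-2017 and describes enrolment in the past tense (section 3.3), so much of the coding may be done, and retrospective reclassification in an open-label study carries its own bias. For those events, report all four categories unpooled with the 6.2.1 definitions in a footnote. If both wordings come into use, the tables should say which applied.

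The cost is minor: protocol and eCRF-guideline wording, an SAP sentence and a table footnote. No new data are needed.

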# 6.2.2 Anticipated Adverse Events in Subjects

Due to the GI complications inherent in CF patients, the identified risks are upper abdominal pain, bloating, constipation, diarrhea, flatulence, heartburn, indigestion, nausea, steatorrhea (fatty stool), vomiting, weight decrease and headache.

# 6.3 Unanticipated Adverse Device Effects

An unanticipated adverse device effect (UADE) is any serious adverse effect on health or safety, any life-threatening problem or death caused by, or associated with a device, if that effect, problem, or death was not previously identified in nature, severity, or degree of incidence in the application; or any other unanticipated serious problem associated with a device that relates to the rights, safety, or welfare of subjects.

An UADE is analogous to a serious adverse event (SAE), defined as any AE, occurring at any exposure to the therapeutic agent, that results in any of the following outcomes:

Title: Absorption and Safety with Sustained Use of Relizorb™ Evaluation (Assure) Study in Patients With Cystic Fibrosis Receiving Enteral Feeding

death, life-threatening AE, inpatient hospitalization or prolonged existing hospitalization, a persistent or significant disability or incapacity or a congenital anomaly/birth defect.

An UADE is defined as "any serious adverse effect on health or safety or any life-threatening problem or death caused by, or associated with, a device, if that effect, problem, or death, was not previously identified in a nature, severity or degree of incidence in the investigational plan or application (including a supplementary plan or application), or any other unanticipated serious problem associated with a device that relates to the rights, safety, or welfare of subjects" according to 21 Code of Federal Regulations Part 812.3.

As provided by the International Conference of Harmonization (ICH) criteria, a serious adverse effect (event) is any clinical event or condition that is:

- Fatal
- Life-threatening
   (Note: The term "life-threatening" refers to any AE that, as it occurs, puts the subject at immediate risk of death. It does not refer to an AE that hypothetically might have caused death if it were more severe.)
- Requires hospitalization or prolonged current hospitalization (not including hospitalization for a pre-existing condition that has not increased in severity or frequency from the subject's underlying medical condition prior to entry into the study)
- Results in persistent or significant disability/incapacity
- A congenital anomaly/birth defect
- Judged to be medically significant by the Investigator
   (Note: A medically significant AE is a medical event that may not be immediately
   life-threatening or result in death or hospitalization but may jeopardize the subject
   or require intervention to prevent one of the outcomes listed above).

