9.1.2 Serious adverse events

Serious Adverse Events (SAEs) will be listed separately but not summarized.

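### The protocol uses UADE in more than one sense, so some serious non-fatal events have no defined expedited report or count trigger; separately, the SAP's AE incidence table leaves out serious events

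*Protocol*

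**What the plan says.** Protocol 6.3 states the regulatory definition twice. A UADE is "any serious adverse effect on health or safety, any life-threatening problem or death caused by, or associated with a device", on condition that it "was not previously identified in nature, severity, or degree of incidence in the application". Between the two statements stands: "An UADE is analogous to a serious adverse event (SAE"), followed by a clause covering any AE with one of a list of serious outcomes. Protocol 6.2 defines an AE without regard to cause. Protocol 6.1 expects complaints that subjects volunteer, or that staff elicit, to make up most UADEs.

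Protocol 6.2.2 says "the identified risks are upper abdominal pain, bloating, constipation, diarrhea" and goes on to further terms, 12 in all, with no severity or frequency for any of them.

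Protocol 7.2.1 has UADEs reviewed in aggregate every 30 days. It calls for contact with the DSMB chair on any death, on two occurrences of the same UADE that the site investigator attributes to Relizorb, on "more than three occurrences of the same UADE regardless of causality", or on a trend in similar UADEs. Protocol 6.4 requires the site's UADE form within 24 hours.

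SAP 9.1 takes UADEs and SAEs out of the AE summaries and says that both will be summarized on their own. SAP 9.1.2 says: "Serious Adverse Events (SAEs) will be listed separately but not summarized".

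**The concern.** A term that drives expedited reporting, aggregate review and DSMB contact should pick out the same events at every site. Here one site can follow the regulatory text and another the SAE sentence, and they will report different events under the same name. UADEs are also a named safety endpoint, so the endpoint count moves with the reading.

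The events most exposed are serious cases of the listed gastrointestinal terms or of weight decrease. These are plausible in this study, because enzyme replacement with tube feeds is withdrawn for 90 days (Protocol 1.0).

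On the reporting side, a reader of the AE table by system organ class and preferred term (SOC/PT) would take it as the incidence of each event. As planned, it gives the incidence of the non-serious ones only.

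**Working it through.** The plan states no figure on this point, so the check is mainly a comparison of passages.

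**1. The senses of UADE**

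- *Narrow* (Protocol 6.3, both regulatory statements): serious, device-associated, and not previously identified in nature, severity or incidence.
- *Broad* (Protocol 6.3, middle sentence, with 6.2): any AE with a serious outcome. Neither device association nor unexpectedness is needed.
- *Loose* (Protocol 6.1): mostly ordinary medical complaints, which fits neither of the other two.
- Within 6.3, the outcome list attached to the middle sentence also omits the medically significant category, which the ICH-based list later in the section includes.

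**2. What depends on the term**

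- Written for UADEs: the 24-hour site form (6.4), the Chief Medical Officer's 24-hour evaluation (4.8.1), the 30-day follow-up (4.2, 4.3), the 30-day aggregate review, and the two count triggers and the trend trigger (7.2.1).
- Independent of the term: any death (7.2.1); any event leading to withdrawal, reported within 24 hours (6.4); continual safety monitoring (4.8.1); and a teleconference if the Chief Medical Officer or DSMB chair has a safety concern (7.2.1).
- The protocol has no SAE reporting rule and no SAE trigger.

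**3. Tracing one event**

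Take a hospitalisation for abdominal pain that is not fatal and does not lead to withdrawal.

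- Broad sense: it is a UADE, and everything in step 2 applies.
- Narrow sense: it depends on whether the event was previously identified. Section 6.2.2 names the term without severity or incidence, so a site could answer either way. If the site treats it as anticipated, or as not device-associated, it is not a UADE, and no defined report or count trigger applies.

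**4. Illustration of the count trigger (risks assumed)**

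Inputs: n = 35 planned subjects (Protocol 4.1), at most one event per subject, and per-subject risk p of one serious listed term. The documents give no p.

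Broad sense: P(more than 3) = 1 − Σ(k = 0 to 3) C(35, k) p^k (1 − p)^(35 − k)

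| Assumed p | P(at least 4 of 35) |
|---|---|
| 0.02 | 0.5% |
| 0.05 | 9.6% |
| 0.10 | 46.9% |
| 0.15 | 79.1% |
| 0.20 | 93.9% |

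For p = 0.05 the four terms are 0.166 + 0.306 + 0.274 + 0.158 = 0.904, leaving 0.096.

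If sites class every such event as anticipated or not device-associated, the count is 0 at every p. That zero follows from the classification and is not an estimate.

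**5. The SAP tables**

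| Event | AE SOC/PT table (14.3.1.2) | Own SOC/PT table | Elsewhere |
|---|---|---|---|
| Non-serious AE | yes | not needed | overview 14.3.1.1, listing |
| UADE | excluded by 9.1 | 14.3.2.1 to 14.3.2.3 | overview, listing |
| SAE not classed as UADE | excluded by 9.1 | none planned in 12.1 | overview, Listing 16.2.6.5 |

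If x subjects had only non-serious events of a term and y had only serious ones, Table 14.3.1.2 shows x/N instead of (x + y)/N. Each such subject removes 1/N: 1/35 = 2.9 percentage points, or 1/40 = 2.5 to 1/30 = 3.3 over the 30 to 40 subjects in SAP 3.3.

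**The case against.** The other side has good points.

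- The regulatory definition is given twice, with a citation, and the clause after the SAE wording can be read as defining SAE rather than UADE. On that view the middle sentence is loose drafting, not a rival definition. That reading is fair, but 6.1 uses the term more loosely still, and nothing tells a site which sense governs.
- A reader might infer that a trigger counting UADEs whatever their cause makes sense only if UADE means SAE. The documents do not support that. The narrow definition covers effects associated with the device as well as caused by it, and causality is a separate rating by the site investigator (6.2.1). The trigger, and tables of UADEs by relationship, can be coherent under the narrow sense.
- A serious case of a listed term may still be unanticipated in severity, and a cluster in incidence. This is correct. The gap arises only where a site decides otherwise, and 6.2.2 gives it nothing to decide by.
- A reader might infer that such events would go unreviewed, or that only UADEs are reported within 24 hours. Neither holds: step 2 of the working lists the routes that do not depend on the term. What is missing is a defined, mandatory route.
- SAEs are counted in the overview table and listed individually. In a study of about 35 subjects with descriptive safety analysis, a separate SAE table is partly presentation. But that does not remove the contradiction between 9.1 and 9.1.2, or restore serious events to the incidence table.

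**Conclusion.** The point stands in two limited parts.

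First, UADE does not have one meaning in the protocol, and the expedited form, the aggregate review and the count triggers rest on it. The gap concerns serious, non-fatal events that do not lead to withdrawal and that a site treats as anticipated or not device-associated. It would be too much to say that every serious event other than death is affected. Serious, device-associated, previously unidentified effects are UADEs on either the narrow or the broad reading, and events leading to withdrawal reach the sponsor within 24 hours regardless. How many events fall in the gap cannot be computed from the documents, and the probabilities in the working rest on assumed risks.

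Second, the SAP contradicts itself on summarizing SAEs. Its AE SOC/PT table omits serious events, by 2.5 to 3.3 percentage points of a term's incidence for each subject whose only event of that term was serious. An SAE not classed as a UADE appears only in the overview table and a listing. This part follows from the text without any assumed rate.

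**What to change.** In the protocol, reconcile 6.1, 6.3, 6.4 and 7.2.1 so that UADE and SAE are separate terms with one definition each. State for each report, review and trigger which category it counts, including whether serious events considered anticipated or unrelated are in or out. Which events belong under each trigger is for the sponsor and the DSMB to settle.

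In the SAP, include SAEs and UADEs in the AE SOC/PT incidence tables, add an SAE table by SOC/PT, and remove the contradiction between 9.1 and 9.1.2.

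The cost is wording in both documents plus one table. No further data collection is needed for the SAP part, since SAEs are already to be listed, and the 30-day reviews already take place.
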